6. ANALYSIS POPULATIONS

6.1. PER PROTOCOL POPULATION

The Per Protocol Population is defined as all subjects who have completed a minimum of 100 EDs with Optivate®. The Per Protocol Population is the primary population for the analysis of efficacy endpoints.

Note: If antifibrinolytic agents have been administered during surgery, the surgery exposure days will not be included in the Optivate® ED calculations.

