8 OUTCOME MEASURES

8.1 Efficacy Measures

All subjects who received at least one dose of Optivate® will be included into the efficacy analysis.

If subjects suffering with severe haemophilia A with a basal FVIII of < 2% are recruited into the study, as per the CHMP guidelines¹², in addition to the analysis for all subjects, separate analyses will also be conducted for subjects with a basal FVIII of < 1% and then for subjects with a basal FVIII of < 2%.

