9 SUBJECT WITHDRAWAL

Subjects may stop study treatment for any of the following reasons:

• Withdrawal of consent.

- Significant protocol deviation.
- Lost to follow-up.
- Incidental illness.
- Occurrence of adverse events (AEs) not compatible with the continuation of the subject's participation in the study, in the Investigator's opinion (*eg* anaphylactic or other severe/serious reaction to infusion, development of inhibitor).
- Investigator's request.
- Requirement for therapeutic intervention prohibited by the protocol *eg* FVIII containing product or antifibrinolytics agents (expect during surgery).
- Premature termination of the trial by BPL on account of an unacceptable risk-benefit ratio. If this occurs, BPL or BPL's representatives will notify the regulatory authorities, ethics committees and Investigators of the reason for premature study termination, within 15 days from the study being halted.
- Subject/guardian is unco-operative and non-compliant with respect to provisions of the protocol.
- Trial stopped by BPL as 10 evaluable subjects have 100 EDs with Optivate[®].
 NB:this may mean that the last two subjects enrolled into the study may receive a shorter treatment period.

The clinical Investigator may also remove a subject if, in his/her opinion, it is in the best interests of the subject.

Subjects are free to withdraw from the study at any time without providing reason(s) for withdrawal and without prejudice to further treatment. The reason(s) for withdrawal will be documented where possible, particularly where withdrawal is a consequence of an adverse event. The subject's primary care physician (where applicable) will be informed of the reason for withdrawal.

Data collected up until a subject's withdrawal from the study, including data for screen failures, will be retained on the clinical database and used in the analysis and clinical study report.

Subjects withdrawing from the study will be requested to complete the same final assessments as subjects completing the study according to the protocol, particularly safety assessments (see Section 7.4). If there is a medical reason for withdrawal, the subject will remain under the supervision of the Investigator until in satisfactory health or the subject's condition has stabilised.

Reasonable efforts will be made to contact subjects who are lost to follow-up. These efforts must be documented in the subject's medical records.

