10.3 Statistical and Analytical plans

All tables, figures and listings will be produced using the most recent version SAS (Statistical Analysis System).

Unless otherwise stated, categorical data will be presented using counts and percentages, whilst continuous variables will be presented using the mean, 95% confidence interval for the mean, standard deviation (SD), median, minimum, maximum, number of subjects (n) and number of missing subjects or datapoints. Minima and maxima will be quoted to the number of decimal places as recorded in the CRF; means, and medians will be quoted to one further decimal place. SDs will be quoted to one further decimal place than the mean value. Percentages will be rounded to one decimal place.

The efficacy analysis will be performed for the per protocol population, and the safety population will be used to report all safety data, in accordance with the statistical analysis plan (SAP). Demographic data will be reported for the safety population.

All data will be listed. More information is in the SAP for the study.

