10.4 Analysis Populations

The following analysis populations will be defined for this study.

If subjects suffering from severe haemophilia A with basal FVIII values of < 2% rather than < 1% are recruited into the study, in addition to the analysis for all subjects, two separate analyses will be conducted: One for subjects with a basal FVIII < 1%, the other for subjects with a basal FVIII < 2%.

Safety Population

The safety ITT population will be defined as all subjects who received at least part of one dose of Optivate[®]. Safety data will be analysed up to the point of withdrawal for subjects who withdraw, if the number of points is adequate to allow a scientific analysis.

Per Protocol Population

The per protocol population will be defined as all subjects who have completed a minimum of 100 EDs with Optivate[®].

NOTE: If antifibrinolytic agents have been administered during surgery, the surgery exposure days will not be included in the Optivate[®] ED calculations.

The efficacy analysis will include all the subjects in the per protocol population. The secondary analysis will include all subjects in the ITT population.

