6.2. SAFETY POPULATION

The Safety Population is defined as all subjects who received at least part of one dose of Optivate[®]. The Safety Population will be used for all analyses of safety endpoints, and as a secondary population for the analysis of efficacy endpoints.

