9. EFFICACY

9.1. PRIMARY EFFICACY ENDPOINT AND ANALYSIS

The primary efficacy endpoint is the assessment of immunogenicity of Optivate® by monitoring plasma inhibitor levels for at least 100 EDs for each subject.

Pre-bolus blood samples for quantitative assays will be collected at the Screening Visit, Baseline Visit (Visit 1), Visit 2, Visit 3, the End of Study Visit (Visit 4) and possibly also at unscheduled visits if deemed necessary.

Inhibitor screen data will be listed only.

Quantitative inhibitor results will be listed.

Summaries of quantitative inhibitor levels will be based on both the Per Protocol and Safety populations.

At each visit, the number and percentage of subjects with positive (\geq 0.6 Bethesda Units) and negative (< 0.6 Bethesda Units) results will be summarised.

Shift tables cross tabulating positive/negative status (based on the Bethesda assay) at the Baseline Visit against those at Visits 2, 3 and 4 will be presented. Shifts from the Baseline Visit to any unscheduled visits will also be summarized. Note, should a subject have more than one unscheduled visit then the worst case assessment (positive) will be used in the summary.

The number of exposure days until development of inhibitors (positive status) will be summarized.

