16. INDEX OF TABLES

- Table 14.1.1 Subject Disposition, All Screened Subjects
- Table 14.1.2 Study Duration, Safety Population
- Table 14.1.3 Demographics and Baseline Characteristics, Safety Population
- Table 14.1.4 Medical History, Safety Population
- Table 14.1.5.1 Prior Medications, Safety Population
- Table 14.1.5.2 Concomitant Medications, Safety Population
- Table 14.2.1.1 FVIII Inhibitor Status, Per Protocol Population
- Table 14.2.1.2 FVIII Inhibitor Status, Safety Population
- Table 14.2.1.3 Shifts in FVIII Inhibitor Status, Per Protocol Population
- Table 14.2.1.4 Shifts in FVIII Inhibitor Status, Safety Population
- Table 14.2.1.5 Number of Exposure Days Until the Development of Inhibitors (Positive Status), Per Protocol Population
- Table 14.2.1.6 Number of Exposure Days Until the Development of Inhibitors (Positive Status), Safety Population
- Table 14.2.2.1 Recovery of Current Factor VIII and First Dose of Optivate, Per Protocol Population
- Table 14.2.2.2 Recovery of Current Factor VIII and First Dose of Optivate, Safety Population
- Table 14.2.3.1 Optivate Recovery (IU/dL per IU/kg) by Visit, Per Protocol Population
- Table 14.2.3.2 Optivate Recovery (IU/dL per IU/kg) by Visit, Safety Population
- Table 14.2.3.3 Optivate Recovery (IU/dL per IU/kg) by Batch, Per Protocol Population
- Table 14.2.3.4 Optivate Recovery (IU/dL per IU/kg) by Batch, Safety Population
- Table 14.2.3.5 Optivate Recovery (IU/dL per IU/kg) by Subject, Safety Population
- Table 14.2.4.1 Bleeds by Subject, Per Protocol Population
- Table 14.2.4.2 Bleeds, Per Protocol Population
- Table 14.2.4.3 Bleeds by Subject, Safety Population
- Table 14.2.4.4 Bleeds, Safety Population
- Table 14.2.5.1 Investigator's Assessment of Effectiveness of Optivate, Per Protocol Population
- Table 14.2.5.2 Investigator's Assessment of Effectiveness of Optivate, Safety Population
- Table 14.2.6.1 Subject's Assessment of Effectiveness of Optivate ,Per Protocol Population
- Table 14.2.6.2 Subject's Assessment of Effectiveness of Optivate, Safety Population
- Table 14.2.7.1 Optivate Exposure Days, Per Protocol Population
- Table 14.2.7.2 Optivate Exposure Days, Safety Population
- Table 14.2.7.3 Total Optivate Dose, Per Protocol Population
- Table 14.2.7.4 Total Optivate Dose, Safety Population
- Table 14.2.7.5 Total Optivate Infusions, Per Protocol Population
- Table 14.2.7.6 Total Optivate Infusions, Safety Population
- Table 14.2.7.7 Optivate Dose per Infusion, Per Protocol Population

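### The primary inhibitor result is taken from subjects who completed 100 exposure days, so an inhibitor case that stops earlier is left out because of its outcome

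*SAP*

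**What the plan says.** SAP 5.1 and 9.1 make the assessment of immunogenicity, by inhibitor testing over at least 100 EDs, the primary efficacy endpoint. SAP 6.1 admits to the Per Protocol Population only subjects with 100 or more EDs and states: "The Per Protocol Population is the primary population for the analysis of efficacy endpoints". SAP 6.2 uses the Safety Population (anyone given at least part of a dose) for safety endpoints and "as a secondary population for the analysis of efficacy endpoints". Neither section keeps an early inhibitor case in the Per Protocol set.

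For the inhibitor endpoint itself, SAP 9.1 adds: "Summaries of quantitative inhibitor levels will be based on both the Per Protocol and Safety populations". The index in SAP 16 accordingly has paired tables for status, shifts and onset. One of them is Table 14.2.1.5, "Number of Exposure Days Until the Development of Inhibitors (Positive Status), Per Protocol Population".

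The protocol gives two answers on the efficacy population. Section 10.3 says "The efficacy analysis will be performed for the per protocol population" and section 10.4 says "The efficacy analysis will include all the subjects in the per protocol population", with a secondary analysis on all treated subjects. Section 8.1 says that all subjects with at least one dose "will be included into the efficacy analysis". SAP 12 reports no changes from the protocol.

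Protocol 9, repeated in SAP 4.1, lists adverse events that may end participation and gives as examples "anaphylactic or other severe/serious reaction to infusion, development of inhibitor".

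**The concern.** Membership of the primary set depends on something that happens after treatment starts and that the endpoint itself can cause. A subject who develops an inhibitor and stops cannot reach 100 EDs and so leaves both numerator and denominator of the primary result. A subject without an inhibitor has no such reason to leave. The Per Protocol status, shift and onset tables therefore lean towards no inhibitors whenever any case stops early. Table 14.2.1.5 can show an onset before 100 EDs only in subjects who carried on to 100.

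The replacement rule (Protocol 4.1 and 5.1, SAP 4.1) does not help. Once more than two subjects withdraw before 100 EDs, replacements are enrolled, and inhibitor withdrawals are not exempt.

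Immunogenicity is the primary objective. The table labelled primary could show no inhibitors while the all-treated table shows one, with nothing in the SAP to say which governs the conclusion.

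**Working it through.** **The plan's own figure.** Twelve enrolled for 10 evaluable is an agreed number, not a calculation (Protocol 10.8, SAP 4.3): 12 − 2 = 10. No inhibitor rate, alpha or power is stated, so there is nothing further to reproduce.

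**Can a case be found before 100 EDs?** Inputs are the visit ranges (Visit 2 at 10–15 EDs, Visit 3 at 50–75 EDs) and three doses a week.
- Positive at Visit 2: 100 − 15 = 85 to 100 − 10 = 90 further EDs. Divided by 3, that is about 28 to 30 weeks.
- Positive at Visit 3: 100 − 75 = 25 to 100 − 50 = 50 further EDs, or about 8 to 17 weeks.

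A positive subject must stay on treatment that long to count in the primary set.

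**One case (assumed scenario).** Twelve treated, one case stops early, 11 reach 100 EDs. Exact (Clopper–Pearson) 95% intervals:
- Per Protocol: 0/11 = 0% (0 to 28.5%).
- Safety: 1/12 = 8.3% (0.2 to 38.5%).

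**Expected bias.** Let p be the true inhibitor risk and w the share of cases that stop before 100 EDs. The documents give neither. Assume every non-case reaches 100 EDs. The expected Per Protocol rate is then p(1−w) / [p(1−w) + (1−p)].

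| True risk p | w = 0 | w = 0.5 | w = 0.8 |
|---|---|---|---|
| 1% | 1% | 0.5% | 0.2% |
| 5% | 5% | 2.6% | 1.0% |
| 10% | 10% | 5.3% | 2.2% |
| 20% | 20% | 11.1% | 4.8% |

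For example, p = 5% and w = 0.5 gives 0.025 / (0.025 + 0.95) = 2.6%.

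**Chance that the primary table shows none although a case occurred.** With 12 treated:
- Joint probability: [1 − p(1−w)]^12 − (1−p)^12.
- Probability of at least one case: 1 − (1−p)^12.
- Conditional probability: the first divided by the second.

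At w = 0.5:

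| p | At least one case | Per Protocol shows none, given a case | Both together |
|---|---|---|---|
| 1% | 11.4% | 48.6% | 5.5% |
| 5% | 46.0% | 43.0% | 19.8% |
| 10% | 71.8% | 35.9% | 25.8% |

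**The case against.** The strongest reply is that a case could not be hidden. A value of 0.6 BU or more is notified to the sponsor at once (Protocol 7.9.2), and a developed inhibitor is automatically serious (SAP 5.3). The subject would appear in Safety Tables 14.2.1.2, 14.2.1.4 and 14.2.1.6, in the serious adverse event tables and in the listings. SAP 5.3 also lists the inhibitor as a safety endpoint, which under SAP 6.2 calls for the Safety Population. SAP 9.1 names both sets without ranking them, whereas SAP 9.2.2 does rank them for recovery. There is no hypothesis test and no planned interval for the inhibitor proportion. This all stands, and it limits the harm. It does not settle which result is primary: the same endpoint has two population roles and the SAP does not say which leads. With no test, the descriptive count is the primary result.

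Stopping is also discretionary, and the protocol provides for extra testing and monitoring of suspected or confirmed cases. That stands too: at w = 0 there is no bias, and no passage supports a particular w.

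The higher risks in the tables may be too pessimistic. Protocol 2 reports no inhibitors in 130 patient-years in previously treated patients, giving an exact Poisson 95% upper limit of 3.69/130, about 2.8 per 100 patient-years. If this population is similar and each subject contributes at most a year, p of 5% or more lies above that limit. At p = 2.8% and w = 0.5, the chance that a case occurs and Per Protocol shows none is 0.986^12 − 0.972^12 = 0.844 − 0.711, about 13%. That is a fair limit on the frequency of the problem, not on its effect when it happens.

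Finally, the all-treated set includes subjects with fewer than 100 EDs, such as the last two enrolled, counted as event-free on partial exposure. Adding early cases to Per Protocol while leaving out short-exposure non-cases would itself push the rate upwards. Both points are reasons to show the two sets side by side.

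**Conclusion.** The concern holds. By the wording of SAP 6.1 and Protocol 10.3 and 10.4, an inhibitor case that stops before 100 EDs is excluded from the primary analysis of the primary endpoint because of that endpoint. In the one-case illustration this turns 8.3% (1/12) into 0% (0/11). If half of cases stop early, the expected Per Protocol rate is roughly half the true risk for the risks shown. These sizes rest on assumed p and w and on all non-cases completing 100 EDs. The direction of the bias does not depend on the assumed values, provided some cases stop early and non-cases complete.

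The case is missing from the primary result, not from the report. This should be fixed, but the planned Safety tables keep it from being more serious. The conflict between Protocol 8.1 and Protocol 10.3 and 10.4 needs resolving in any event.

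**What to change.** - In SAP 6.1 and 9.1 and Protocol 10.3 and 10.4, name the Safety Population as primary for the inhibitor endpoint and Per Protocol as supportive. Other efficacy endpoints can stay as they are.
- State that a subject with a confirmed inhibitor at any ED is evaluable and counts as an event, including in the Per Protocol inhibitor tables. Footnote how those subjects entered the set.
- Say whether such a subject also counts towards the 10 subjects with 100 EDs agreed with the regulator, or whether that exposure target is kept separate.
- Bring Protocol 8.1 into line with Protocol 10.3 and 10.4 and SAP 6.1.

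No change to the withdrawal rule is proposed. The cost is wording, because both sets of inhibitor tables are already planned. The headline figure may look slightly less favourable. Because some treated subjects will have under 100 EDs of follow-up, the Per Protocol table should stay beside the all-treated one.

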6.2. SAFETY POPULATION

The Safety Population is defined as all subjects who received at least part of one dose of Optivate[®]. The Safety Population will be used for all analyses of safety endpoints, and as a secondary population for the analysis of efficacy endpoints.

6.3. OTHER ANALYSIS SETS

If subjects suffering from severe haemophilia A with basal FVIII values of < 2% rather than < 1% are recruited into the study, in addition to the analysis for all subjects, two separate analyses will be conducted: One for subjects with a basal FVIII < 1%, the other for subjects with a basal FVIII $\ge 1\%$.

6.4. PROTOCOL DEVIATIONS

Protocol deviations will be identified from the deviations log compiled by the study monitors. Further deviations may be identified from the clinical database. Deviations will be identified prior to database lock, and will be listed only.

Sponsor: BPL

Protocol: 8VWF07

Version: 1.0

Statistical Analysis Plan

7. GENERAL ASPECTS FOR STATISTICAL ANALYSIS

7.1. GENERAL METHODS

Statistical outputs will be generated using SAS version 9.3 (or later).

The study only has one treatment and so all summary tables will have a single results column for Optivate[®]. However, if subjects suffering from severe haemophilia A with basal FVIII values of < 2% rather than < 1% are recruited into the study, an additional two results columns will be presented, one for subjects with a basal FVIII < 1%, and one for subjects with a basal FVIII $\ge 1\%$ (see Section 6.3).

Continuous variables will be summarised using the number of observations (n), mean, 95% confidence interval for the mean, standard deviation (SD), median, minimum, and maximum. Minima and maxima will be quoted to the number of decimal places as recorded in the CRF, means and medians will be quoted to one further decimal place, and SDs will be quoted to one further decimal place than the mean value. Categorical variables will be summarised using number of observations (n), frequency and percentages of subjects. Percentages will be rounded to one decimal place, with the exception of 0% and 100%, which will be presented to no decimal places.

All relevant subject data will be included in listings. All subjects entered into the database will be included in subject data listings.

Data from unscheduled visits will not be included in the summary tables. These data will be listed only.

Where multiple data/results are available at a given visit for the same parameter, the first non-missing result will be used in the summary tables. All data will however be listed.

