6 INVESTIGATIONAL MEDICINAL PRODUCT

At Baseline Visit (V1), eligible subjects will receive a bolus dose of Optivate[®] (30 IU/kg) for recovery assessments. Bolus doses (30 IU/kg) will also be administered at V2, V3, and V4.

Following V1, subjects will start home therapy using Optivate[®] prophylactically at a dose between 20-40 IU/kg administered three times a week for at least 100 EDs.

As a part of home therapy, subjects will also administer Optivate[®] for preventative use (prior to physiotherapy or increased physical activity) or to treat break through bleeds. This will be at a dose agreed with the Investigator and in accordance with the Summary of Product Characteristics (SmPC)¹ for Optivate[®]. Excessive bleeding may require treatment at the Investigational site.

CONFIDENTIAL

Page 22 of 100

If the subject requires surgery this can be conducted under the cover of $Optivate^{\mathbb{R}}$, using doses as recommended in the SmPC¹, also see Section 6.2.3.

All doses will be to the nearest 1 mL, except for the bolus doses at the Baseline Visit (V1), Visit 2 (V2), Visit 3 (V3) and End of Study Visit (V4) which will be to the nearest 0.1 mL.

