7.7.1 Excessive Bleeding Visit or After an Emergency Bleed

During home therapy subjects will assign bleed severity as major, minor and emergency, where a major bleed is defined as a bleed that unacceptably restricts the patient's day-to-day life and an emergency bleed is one which requires immediate medical attention. Also see Section 7.6.

If any subject is concerned about their treatment or has excessive bleeding or an emergency bleed they must contact the Investigational site.

If the subject has recently had surgery and the excessive bleeding is a result of the surgery this will be recorded in the CRF as an adverse event.

If required the subject will attend the Investigational site, and the following procedures will be conducted:

- Review of changes since the last visit (*eg* AEs).
- Blood samples will be collected for:
 - FVIII:C assay. Samples will be assayed at the central and local laboratory, to help manage the subject locally until the central results are made available. Also see Section 7.9.1 and for further details the Laboratory Manual.

- FVIII inhibitor screen and Nijmegen-Bethesda assay (see Section 7.9.2).
- The Investigator must assess the bleed severity and efficacy of Optivate[®] in treating the bleed (see Sections 7.6, 7.8 and 8.1.2.3).

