7.8 Study Diaries

After the screening assessments have been conducted all subjects will be given a study diary to use during the study. The study diary is to enable comprehensive record of health information consistently for all subjects. In addition, subjects will be provided with a study diary manual explaining how to record the data and how this data needs to be returned to the site for regular review (see the study diary manual for more details).

The study diaries are to be completed when the subject has an adverse event or takes Optivate[®] or other medication (except herbal and homeopathic remedies) at home or at a local clinic (*ie* not the Investigational site) and with bleed details.

The diaries will record the following information:

- Optivate usage (home or at a local clinic).
- Details of any other AEs which occurred during home therapy. AEs that occur at site will be recorded on the CRF by the site staff; these will not be entered into the study diary to avoid duplication.
- Details of concurrent medication (excluding vitamins and herbal and homeopathic remedies) including name (preferably the generic name), dose, start date and stop date.
- Details of bleeds:
 - Duration (bleed start and stop time)
 - Location (joint, muscle or open/other).
 - Severity (major, minor or emergency). A major bleed is defined as a bleed that unacceptably restricts the patient's day-to-day life and an emergency bleed requires

urgent medical attention. In the case of emergency bleeds the study centre will be contacted. Clinicians will also review this data regularly and amend if necessary after discussing it with the subject (see Section 7.6).

- New bleed or ongoing bleed
- Cause (spontaneous bleeding, injury or other).
- Subjects will assess Optivate[®] therapy for each bleed as:
 - Very Helpful
 - o Helpful
 - Helped a little
 - Did not help
- The Investigator will also be assess Optivate[®] therapy for each bleed as:
 - Excellent
 - o Good
 - Moderate
 - o Poor

The study diaries will also record the following details of each dose of Optivate[®] administered at home or at the local clinic:

- Date and time of dose.
- Batch number.
- Whether the dose was administered as a preventative dose, a routine prophylactic dose or to treat a bleed.

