7.3. MISSING DATA

All available data will be used in the statistical analysis. There will be no imputation for missing data.

Sponsor: BPL

Protocol: 8VWF07

Version: 1.0

Statistical Analysis Plan

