9.2.4. Optivate® Exposure Days

An exposure day is defined as a day in which the subject has received at least one dose of Optivate[®]. The number of exposure days will be listed for each subject. Descriptive statistics will be presented for the number of exposure days per subject.

For each subject the number of exposure days per month and the number of exposure days per year will be calculated as follows:

Number of exposure days per year = $\frac{\text{Number of exposure days captured during the study}}{\text{Time on study}} \times 365$

Number of exposure days per month = Number of exposure days captured during the study x 28

Time on study

where time on study = Date of Visit 4 (end of study visit)/withdrawal visit - Date of Baseline visit + 1

These will also be summarised.

Summaries of exposure days will be based on both the Per Protocol Population and Safety Population. NB: In the case of treatment for surgery, if anti-fibrinolytic agents have been administered (pre or post surgery) then these exposure days will be excluded from the Optivate® exposure day calculation.

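### SAP 7.1 confines all unscheduled-visit data to listings, which conflicts with the dose, exposure-day, adverse-event and time-to-inhibitor summaries, and the SAP does not say which rule governs

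*SAP*

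**What the plan says.** SAP 7.1 sets a general rule: "Data from unscheduled visits will not be included in the summary tables. These data will be listed only". It names no data type and no class of table. SAP 9.1 makes one exception, for inhibitor status: "Shifts from the Baseline Visit to any unscheduled visits will also be summarized", taking the worst case if a subject has several such visits. The same section then adds "The number of exposure days until development of inhibitors (positive status) will be summarized" and does not mention unscheduled visits.

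Other parts of the SAP point the other way. SAP 7.3 says "All available data will be used in the statistical analysis". SAP 9.2.3 counts break-through bleeds in total and names emergency bleeds. SAP 9.2.4 says "An exposure day is defined as a day in which the subject has received at least one dose of Optivate", and removes only surgery days on which antifibrinolytics were given. SAP 9.2.5 totals doses and infusions overall and by reason for use. SAP 10.2 restricts the adverse-event tables by treatment emergence and by nothing else.

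In the protocol, unscheduled visits are where excessive or emergency bleeds are handled if attendance is required. Section 6 notes: "Excessive bleeding may require treatment at the Investigational site". Section 7.7.1 has adverse events reviewed and inhibitor samples taken there, and adds: "The Investigator must assess the bleed severity and efficacy of Optivate". Section 7.7.2 allows further inhibitor tests and a recovery assessment when an inhibitor is suspected or confirmed. On recording, Section 7.8 says: "AEs that occur at site will be recorded on the CRF by the site staff; these will not be entered into the study diary". The same section limits diary dosing records to Optivate used at home or at a local clinic.

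**The concern.** The exposure, consumption and adverse-event tables are totals over days, infusions and events. They are correct only if every day, infusion and event is counted, whatever visit label it carries. A rule that drops records by visit type makes them incomplete, and those records come from visits made for a clinical reason.

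The primary endpoint is also affected. Inhibitor samples are taken at excessive-bleeding visits and whenever an inhibitor is suspected, so an unscheduled visit is a likely place for a first positive result. The shift table would show that result. The summary of exposure days until inhibitor development has no matching exception, so two tables for the same endpoint could disagree about the same subject.

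**Working it through.** The plan gives no figure to reproduce, so the check is a comparison of text followed by arithmetic for scale.

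**Step 1: which records depend on the unscheduled visit**

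| Record | Diary route? | Source | Effect of SAP 7.1 read literally |
|---|---|---|---|
| Bleed, its severity, subject's rating | Yes | Protocol 7.6, 7.8 | At risk only if the tables draw on the visit record |
| Investigator's rating of treatment | Yes, listed among the diary content for each bleed | Protocol 7.8 | As above |
| Optivate dose at the study site, unscheduled visit | No, the diary covers home and local clinic | Protocol 7.8 | Excluded from SAP 9.2.5 tables |
| Exposure day whose only dose was that one | No | Protocol 7.8 | Excluded from SAP 9.2.4 tables |
| Adverse event occurring at the site, unscheduled visit | No, CRF only | Protocol 7.8 | Excluded from SAP 10.2 tables |
| Adverse event arising at home, reviewed at the visit | Yes | Protocol 7.8, 8.2.1 | Not affected |
| Inhibitor first positive at an unscheduled visit | Not applicable | Protocol 7.7.1, 7.7.2, 8.1.1 | In the shift table; excluded from the time-to-inhibitor summary |
| Doses and adverse events at V1 to V4 | Not applicable | Scheduled visits | Not affected |

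**Step 2: does any text settle the conflict?** No. SAP 7.1 is general and unqualified, and the endpoint sections are specific but silent on unscheduled visits. Protocol 10.7.1 pools CRF and diary adverse events. The protocol contains no exclusion of unscheduled-visit data, yet SAP 12 declares no change from it.

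**Step 3: scale per record.** The inputs are 12 planned subjects, 10 evaluable subjects and 100 exposure days.

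- One subject's only event dropped: 1/12 = 8.3 percentage points, or 1/10 = 10.0 percentage points.
- One exposure day dropped from a count of 100: 1/100 = 1%.
- One inhibitor dated to the next scheduled visit and not to the unscheduled visit where it was found: the planned windows are 10 to 15 exposure days at V2 and 50 to 75 at V3. The delay could therefore be at most 75 − 10 = 65 exposure days between those visits. If no later scheduled sample is positive, the subject would leave the summary altogether.

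**Step 4: total effect.** This would be the per-record effect multiplied by the number of affected records. The documents give no number of unscheduled visits, so it cannot be computed.

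**The case against.** The strongest reply is that SAP 7.1 is a by-visit convention. The text that follows it deals with several results for one parameter at one visit. The bleed, dose and adverse-event tables are not titled by visit, and the usage listings are organised by purpose. The endpoint sections ask for totals, and SAP 7.3 asks for all available data. On that reading nothing is lost. The table mock-ups, which might confirm it, are an attachment that is not part of the documents reviewed.

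This is a reasonable account of what the authors probably meant, and it rules out any claim that data will certainly be lost. It does not remove the ambiguity. SAP 10.2 uses the same term, summary tables, for the adverse-event tables, so the term is not reserved for by-visit displays. The single written exception in SAP 9.1 also suggests that the authors thought the rule would otherwise apply. SAP 15 provides for double programming, and two programmers could each follow the SAP and produce different tables.

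A reader might infer something stronger: that the ratings of the worst bleeds disappear and the efficacy tables are tilted in favour of Optivate. The documents do not support that. Protocol 7.6 and 7.8 put bleeds, their severity and both ratings among the diary data, reviewed between visits and at visits. Attendance after an emergency bleed is conditional on need. Nothing in the documents indicates how bleeds managed at such visits would be rated, so a direction of bias cannot be asserted.

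**Conclusion.** The point holds as an unresolved conflict within the SAP, and it should be corrected. Read literally, SAP 7.1 would exclude site-given doses, the exposure days that rest on them, and adverse events occurring on site, in each case at unscheduled visits only. It would also exclude an inhibitor first detected at an unscheduled visit from the time-to-inhibitor summary, which is the most consequential item because it belongs to the primary endpoint. For bleeds and their ratings there is a risk under the literal reading, not an established loss.

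The size is known only per record: 8.3 to 10 percentage points for one subject-level event with 12 to 10 subjects, and 1% of a 100-day exposure count for one dosing day. These figures assume that the analysis set has 10 to 12 subjects and that the subject has no other qualifying event. The conclusion assumes that records made at unscheduled visits are labelled as such in the database, which the documents imply but do not state.

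**What to change.** Replace the unscheduled-visit rule in SAP 7.1 with:

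> *Unscheduled-visit results are excluded only from by-visit summaries of scheduled laboratory and recovery assessments. Adverse events, bleeds and their severity and efficacy ratings, exposure days, doses and infusions, and the number of exposure days until inhibitor development use all data regardless of visit type. The Section 9.1 unscheduled-visit inhibitor shifts are retained.*

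If the narrow reading was always intended, this text simply states it. The cost is SAP wording and a check that the table mock-ups and programs follow it. The data are already collected and listed, so no protocol change or new data collection is needed.
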